3.1.3 Definition of Dose-Limiting Toxicity

Patients will be closely monitored for adverse events during a DLT assessment period, which starts on Day 1 of Cycle 1 and continues through Day 1 of Cycle 2. *The DLT assessment period is the same for maintenance phase (Arm A) and induction phase (Arm B).* Adverse events meeting criteria for DLT within the assessment period must be

Venetoclax—F. Hoffmann-La Roche Ltd Page 56 of 214 Protocol GO41864, Version 1 reported to the Sponsor within 24 hours. The expected start of Cycle 2 would be on Day 22 if there are no treatment delays. The same DLT criteria will be used in the maintenance and induction settings.

Determination of whether a patient is evaluable for DLT assessment will be made in accordance with the following rules:

- Patients who receive study treatment and remain on study through the DLT assessment period will be considered DLT-evaluable.
- Patients who discontinue from treatment with venetoclax prior to completing the DLT assessment period for reasons other than a DLT will be considered non-evaluable for dose-escalation decisions and MTD determination, and will be replaced by an additional patient at that same dose level.
- Patients who receive less than 50% of planned venetoclax doses during the DLT assessment period will be considered non-evaluable for dose-escalation decisions and will be replaced by another patient in that cohort.

A DLT is defined in this trial as any one of the following events occurring during the DLT assessment period and is assessed by the investigator as possibly being related to study treatment.

The following events will be considered DLTs only if they are associated with treatment delay beyond 14 days in initiating Cycle 2, Day 1:

- Grade 4 thrombocytopenia (platelet count <25,000/mm³)
- Grade 3 thrombocytopenia with severe bleeding
- Grade 4 anemia
- Grade 4 neutropenia (absolute neutrophil count [ANC] < 500/µL)

The following events will be considered DLTs regardless of whether they result in a treatment delay:

- Any treatment-related death
- Grade 3 febrile neutropenia lasting for more than 7 days with growth factor support and supportive care
- Grade 4 febrile neutropenia of any duration
- Grade ≥ 3 diarrhea, nausea, or vomiting lasting for ≥ 72 hours despite adequate treatment and supportive care (e.g., anti-emetics, anti-diarrheals, etc.)

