- Laboratory TLS lasting for ≥ 7 days with best supportive care or clinical TLS according to the Howard criteria (Howard et al. 2011)
- Treatment related Grade ≥ 3 non-hematologic, non-hepatic toxicities lasting for ≥72 hours

- Laboratory abnormalities consistent with Hy's Law will be considered a DLT. Hy's Law is defined as AST and/or ALT elevation > 3 × ULN, in conjunction with an elevation in total bilirubin to > 2 × ULN, without findings of cholestasis (ALP within normal limits), in patients for whom no other cause of hepatotoxicity is evident.
- All study treatment-related adverse events requiring permanent discontinuation of any of the study drugs

3.1.4 Dose-Escalation Rules, Determination of Dose-Limiting Toxicities, and Recommended Phase II Dose

Dose-escalation for venetoclax in the maintenance only (Arm A) as well as in the induction and maintenance (Arm B) settings will occur in accordance with the rules listed below.

Arm A (Refer to Figure 3):

- A minimum of 3 DLT-evaluable patients will initially be enrolled into each cohort.
- If none of the first 3 DLT-evaluable patients experiences a DLT, enrollment of the next cohort at the next dose level may proceed.
- If 1 of the first 3 DLT-evaluable patients experiences a DLT, the cohort will be expanded to 6 patients. If there are no further DLTs in the first 6 DLT-evaluable patients, enrollment of the next cohort at the next dose level may proceed.
- If 2 or more of the first 6 DLT-evaluable patients in the cohort experience a DLT, an additional 3 patients will be evaluated for DLTs at a lower dose level. If none of the first 3 DLT-evaluable patients experiences a DLT, the MTD in maintenance will have been reached.
- If 1 of the first 3 DLT-evaluable patients *at a lower* dose level experiences a DLT, *this* cohort will be expanded to 6 patients. If there are no further DLTs in the first 6 DLT-evaluable patients, the MTD in maintenance will have been reached.
- If 2 or more of the first 6 DLT-evaluable patients in the *lower* dose *level* cohort experience a DLT, the MTD will have been exceeded and dose-escalation in maintenance will stop.
- If the MTD is exceeded at any dose level, the highest dose at which fewer than 2 of 6 DLT-evaluable patients (i.e., ≥ 33%) experience a DLT will be declared the MTD.

If the MTD is not exceeded at any dose level, the highest dose of venetoclax (800 mg) administered in maintenance will be declared the MTD for the maintenance setting.

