Diarrhea, Grade 4	 Withhold venetoclax. Withhold atezolizumab plus carboplatin etoposide. Administer anti-diarrheals per institutional guidelines (e.g., loperamide 4 mg initial dose up to a maximum of 16 mg per day) Upon resolution of Grade 4 diarrhea to Grade ≤ 1: Resume treatment with venetoclax at one dose level reduction (see Table 7) Administer carboplatin and etoposide at 75% of previous dose (see Table 8). Dose of carboplatin and etoposide can be re-escalated (even to full dose) with the approval of Medical Monitor (see Section 5.1.5.2). Administer atezolizumab at previous dose. For uncontrolled Grade 4 diarrhea that occurs despite adequate anti-diarrhea medication or any grade of diarrhea requiring hospitalization: Further reduce venetoclax by one dose level (see Table 7). Administer carboplatin and etoposide at 75% of previous dose (see Table 8).
Hepatic event, Grade 2	 Monitor LFTs more frequently until return to baseline Events of > 5 days duration: Withhold atezolizumab for up to 12 weeks after event onset. Initiate treatment with corticosteroids equivalent to 1–2 mg/kg/day oral prednisone. If event resolves to Grade 1 or better, resume atezolizumab. If event does not resolve to Grade 1 or better while withholding atezolizumab, permanently discontinue atezolizumab and contact Medical Monitor.

Table 10Management Guidelines for Specific Adverse Events with
Venetoclax, Atezolizumab, and Carboplatin Etoposide (cont.)

Table 10 Management Guidelines for Specific Adverse Events with Venetoclax, Atezolizumab, and Carboplatin Etoposide (cont.)

Event	Management	
Hepatic event, Grade 3	 Discontinue atezolizumab. Withhold venetoclax. Withhold carboplatin and etoposide. If hepatic event resolves to ≤ Grade 1: Resume venetoclax at one dose level reduction (see Table 6). Administer carboplatin and etoposide at 75% of previous dose (see Table 8). 	
Hepatic event, Grade 4	Discontinue atezolizumab.Discontinue venetoclax.Discontinue carboplatin and etoposide.	

ANC = absolute neutrophil count; G-CSF = growth-colony stimulating factor.

^a Dose modifications (as specified in the table above) should be made based on ANC and platelet count assessment on Day 1 of each cycle. No dose modifications are required based on ANC and platelet count assessment done on Cycle 1, Day 8 and Cycle 1, Day 15.

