Event	Management
Non-hematologic Toxicity (Not specifically described in Table 9)	
Grade 3 or 4 non-hematologic events	 Delay venetoclax for a maximum of 28 days. First episode: If improvement to Grade ≤ 1 or baseline, resume previous doses of venetoclax. For subsequent episodes: If improvement to Grade ≤ 1 or baseline, restart venetoclax at one dose level reduction. Certain treatment-emergent non-hematologic adverse events (e.g., venous thromboembolic events) may be managed and become clinically stable following medical intervention but may not improve to Grade ≤ 1 according to the NCI CTCAE definitions. In such cases, if a patient is clinically stable, resumption of study drug may be possible after consultation with the Medical Monitor.
Grade 2 related non- hematologic toxicity	 Delay treatment with venetoclax until resolution to Grade ≤ 1 (or baseline status) for a maximum of 28 days. After resolution, resume full dose of venetoclax
Grade 1 non-hematologic toxicity	No dose reduction or delay.

Toxicities associated or possibly associated with atezolizumab treatment should be managed according to standard medical practice. Additional tests, such as autoimmune serology or biopsies, should be used to evaluate for a possible immunogenic etiology.

Although most immune-mediated adverse events observed with immunomodulatory agents have been mild and self-limiting, such events should be recognized early and treated promptly to avoid potential major complications. Discontinuation of atezolizumab may not have an immediate therapeutic effect, and in severe cases, immune-mediated toxicities may require acute management with topical corticosteroids, systemic corticosteroids, or other immunosuppressive agents.

The investigator should consider the benefit–risk balance a given patient may be experiencing prior to further administration of atezolizumab. In patients who have met the criteria for permanent discontinuation, resumption of atezolizumab may be considered if the patient is deriving benefit and has fully recovered from the immune-mediated event. Patients can be re-challenged with atezolizumab only after approval has been documented by both the investigator (or an appropriate delegate) and the Medical Monitor.

PULMONARY EVENTS

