- ^c Resumption of atezolizumab may be considered in patients who are deriving benefit and have fully recovered from the immune-mediated event. Patients can be re-challenged with atezolizumab only after approval has been documented by both the investigator (or an appropriate delegate) and the Medical Monitor.

Table 2	Management Guideline	es for Hepatic Events (cont.)
---------	----------------------	-------------------------	--------

Event	Management
Hepatic event, Grade 3 or 4	 Permanently discontinue atezolizumab and contact Medical Monitor. ^c
	 Consider patient referral to gastrointestinal specialist for evaluation and liver biopsy to establish etiology of hepatic injury.
	 Initiate treatment with corticosteroids equivalent to 1–2 mg/kg/day oral prednisone.
	 If event does not improve within 48 hours after initiating corticosteroids, consider adding an immunosuppressive agent.
	 If event resolves to Grade 1 or better, taper corticosteroids over ≥ 1 month.

LFT = liver function test.

- ^a Atezolizumab may be withheld for a longer period of time (i.e., > 12 weeks after event onset) to allow for corticosteroids (if initiated) to be reduced to the equivalent of ≤10 mg/day oral prednisone. The acceptable length of the extended period of time must be agreed upon by the investigator and the Medical Monitor.
- ^b If corticosteroids have been initiated, they must be tapered over ≥ 1 month to the equivalent of ≤ 10 mg/day oral prednisone before atezolizumab can be resumed.
- ^c Resumption of atezolizumab may be considered in patients who are deriving benefit and have fully recovered from the immune-mediated event. Patients can be re-challenged with atezolizumab only after approval has been documented by both the investigator (or an appropriate delegate) and the Medical Monitor.

GASTROINTESTINAL EVENTS

Immune-mediated colitis has been associated with the administration of atezolizumab. Management guidelines for diarrhea or colitis are provided in Table 3.

All events of diarrhea or colitis should be thoroughly evaluated for other more common etiologies. For events of significant duration or magnitude or associated with signs of systemic inflammation or acute-phase reactants (e.g., increased C-reactive protein, platelet count, or bandemia): Perform sigmoidoscopy (or colonoscopy, if appropriate) with colonic biopsy, with three to five specimens for standard paraffin block to check for inflammation and lymphocytic infiltrates to confirm colitis diagnosis.

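### Section 3.1.3 does not settle whether a patient with a DLT and under half the planned venetoclax doses counts; read literally, the patient is replaced and the DLT leaves the 3+3 count

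*Combined protocol and SAP*

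**What the plan says.** Section 3.1.3 and the synopsis give three consecutive evaluability bullets:

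1. "Patients who receive study treatment and remain on study through the DLT assessment period will be considered DLT-evaluable".
2. Those who stop venetoclax "prior to completing the DLT assessment period for reasons other than a DLT will be considered non-evaluable", both for escalation decisions and for determining the MTD, and are replaced.
3. "Patients who receive less than 50% of planned venetoclax doses during the DLT assessment period will be considered non-evaluable for dose-escalation decisions". They too are replaced in the same cohort.

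Only the second bullet excepts DLTs. No passage ranks the three or says that a patient with a DLT is always evaluable.

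Two items on the DLT list in Section 3.1.3 matter here. The last is "All study treatment-related adverse events requiring permanent discontinuation of any of the study drugs". Another is a treatment-related, non-hematologic, non-hepatic toxicity of Grade 3 or higher that lasts at least 72 hours.

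Section 3.1.4 counts DLT-evaluable patients only. In Arm A, "If 2 or more of the first 6 DLT-evaluable patients in the cohort experience a DLT", three more patients are assessed at a lower dose level. In Arm B the same count means that the MTD has been exceeded and escalation stops.

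The management guidance provides for venetoclax holds in events that can be DLTs:

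- Table 10 (Section 5.1.6.3), Grade 3 hepatic event: "Discontinue atezolizumab. Withhold venetoclax. Withhold carboplatin and etoposide".
- Appendix 13, Table 2, Grade 3 or 4 hepatic event: "Permanently discontinue atezolizumab and contact Medical Monitor".
- Appendix 12, Grade 3 or 4 non-hematologic events: "Delay venetoclax for a maximum of 28 days".

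**The concern.** The second bullet keeps in a patient who discontinues venetoclax because of a DLT. It says nothing about a patient whose venetoclax is only held. The third bullet has no DLT exception at all, so it catches the held patient and, read literally, also the patient who stopped permanently before reaching half the doses. Because one bullet carries the exception and the next does not, a reader could take the omission as deliberate.

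The patients affected are those whose toxicity was early enough to interrupt dosing. Under the literal reading each is replaced by someone who may have no DLT. The same events could then lead one reader to fail a cohort and another to clear it. The Arm A result also sets the maintenance dose used in Arm B, so an undercount there carries forward.

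**Working it through.** **The plan's own figures.** The escalation total of 18–42 in Section 6.1 reproduces as 3 × (2 + 4) = 18 and 6 × (2 + 5) = 42. The MTD threshold in Section 3.1.4 is 2/6 = 33.3%. Neither depends on this point, and the 18–42 range makes no allowance for replacements.

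**When the third bullet applies.** Planned Cycle 1 venetoclax doses are taken from Sections 3.1.2.1 and 3.1.2.2.

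| Schedule | Planned doses | Most doses still under 50% | Hold must start before the dose on |
|---|---|---|---|
| Arm A | 21 | 10 (47.6%) | Day 11 |
| B1–B3 | 7 | 3 (42.9%) | Day 4 |
| B4 | 14 | 6 (42.9%) | Day 7 |

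The hold must then last to the end of planned dosing.

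**Whether the case can arise.**

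- *Hepatic.* A Grade 3 hepatic event ends atezolizumab and suspends venetoclax. If treatment-related, it is a DLT under the last list item. In Arm A, a hold from Day 11 or earlier through Day 21 leaves at most 10 of 21 doses. The first bullet counts this patient; the third replaces the patient.
- *Other non-hematologic.* Such a DLT needs 72 hours. The permitted venetoclax delay of up to 28 days is longer than an undelayed window.
- *Tumor lysis.* Appendix 11 stops further venetoclax until resolution if its laboratory criteria are met within 24 hours of the first dose. Laboratory tumor lysis syndrome lasting at least 7 days is a DLT. In B1–B3 such a hold leaves 1/7 = 14.3% of doses. Section 5.1.4.1 considers this risk low.

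**Effect on one cohort.** Take 1 DLT in the first three patients and 1 in the second three: 2/6. If the later patient is made non-evaluable and the replacement has no DLT, the count is 1/6 and the cohort is cleared. At a true rate p = 1/3 a replacement is free of DLT with probability 1 − 1/3 = 67%.

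**Direction.** All sequences of 10 patients were listed, each patient having no DLT, a counted DLT or an excluded DLT, and those with at least 6 evaluable patients were kept (46,464). Exclusion never raised the count in the first 3 or first 6 evaluable patients. It never blocked an escalation that full counting allowed, and it allowed escalation in 5,415 sequences where full counting did not. These are unweighted sequences, not probabilities.

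**Average effect.** Let f be the share of DLTs that end with under 50% of doses. The documents give neither p nor f, so both are assumptions.

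- Counted rate: p* = p(1 − f)/(1 − pf), which is at most p for any f from 0 to 1.
- Chance of clearing a cohort (0/3, or 1/3 then 0/3): (1 − p*)³ + 3p*(1 − p*)² × (1 − p*)³.
- At p = 1/3 and f = 0: 0.296 + 0.444 × 0.296 = 0.428.
- At p = 1/3 and f = 0.10: p* = 0.300/0.967 = 0.310, and the chance is 0.473.

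| True rate p | f = 0 | f = 0.05 | f = 0.10 | f = 0.25 |
|---|---|---|---|---|
| 1/3 | 0.428 | 0.450 | 0.473 | 0.551 |
| 0.40 | 0.309 | 0.330 | 0.351 | 0.428 |

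A simulation of 400,000 cohorts with replacement at p = 1/3 gave 0.429, 0.473 and 0.552 for f = 0, 0.10 and 0.25.

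**The case against.** The best reply is that the first bullet is a general rule, the other two are exceptions to it, and the second shows that DLT patients are meant to stay in. On that view a clause is missing and no one would misapply the rule. The intent is plausible, but the argument does not settle the reading: if the third bullet is an exception to the first, it is the exception that removes the DLT patient.

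The examples also need more than the guidance dictates. Section 5.1.6.3 applies holds to the component judged the primary cause, and Section 5.1.5 lets the other components continue. Table 10 and Appendix 12 allow venetoclax to resume on improvement, and 28 days is a maximum. A 3-day hold in Arm A leaves 18 of 21 doses. Hematologic DLTs are largely outside the rule: cytopenia DLTs require a delay of more than 14 days in starting Cycle 2, and Table 10 requires no modification for Day 8 or Day 15 counts. All of this stands. The guidance permits the case and does not force it, and f may be small; nothing in the documents supports 0.25 in particular.

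The third bullet also mentions only escalation decisions, not MTD determination. Read that strictly, the patient leaves one count and stays in the other, which is a further mismatch to reconcile.

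Finally, there are safeguards. DLTs are reported within 24 hours, escalation is permitted and not automatic, the Sponsor reviews cumulative safety data, the RP2D draws on aggregate safety data, and the safety population in Section 6.4 keeps every treated patient. They keep the event visible, but they do not return it to the 3+3 count.

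**Conclusion.** The concern holds. The evaluability rules conflict for a patient who has a DLT and receives under half the planned venetoclax doses, and the literal reading removes that DLT from the escalation count. The effect is to lower the count or leave it unchanged. The change from 2/6 to 1/6 needs no assumption about frequency.

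The average size does need one. At a true rate of one third, clearance rises by about 2 points if 5% of DLTs are affected, 4 to 5 points at 10% and 12 points at 25%. Exposure is confined to early, sustained dose loss, and review may catch individual cases. It should be fixed before a cohort decision depends on it.

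**What to change.** In Section 3.1.3 and the matching synopsis text, state that any patient with a DLT in the assessment window is DLT-evaluable regardless of the number of venetoclax doses received. Apply the under-50% non-evaluability and replacement rule only to patients without a DLT. In the same edit, make the second and third bullets agree on whether they cover MTD determination as well as escalation.

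This follows the second bullet's own logic and keeps the purpose of the third, which is to replace under-exposed patients who had no DLT. It costs one clause in two places and no extra patients, and it leaves every dosing and holding instruction unchanged. The only consequence is that some cohorts may show a less favorable DLT count.

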Venetoclax: 200 mg/QD NC on Days 1-7

Atezolizumab: 1200 mg Q3W on Day 1

Carboplatin: AUC 5 mg/mL min (Calvert formula) on Day 1

Etoposide: 100 mg/m² on Days 1-3

Induction Cohort B2 (Dose Level 2):

Venetoclax: 400 mg/QD NC on Days 1-7

Atezolizumab: 1200 mg Q3W on Day 1

Carboplatin: AUC 5 mg/mL min (Calvert formula) on Day 1

Etoposide: 100 mg/m² on Days 1–3

Induction Cohort B3 (Dose Level 3):

Venetoclax: 800 mg/QD NC on Days 1-7

Atezolizumab: 1200 mg Q3W on Day 1

Carboplatin: AUC 5 mg/mL min (Calvert formula) on Day 1

Etoposide: 100 mg/m² on Days 1-3

Induction Cohort B4 (Dose Level 4):

Venetoclax: 800 mg/QD NC on Days 1-14

Atezolizumab: 1200 mg Q3W on Day 1

Carboplatin: AUC 5 mg/mL min (Calvert formula) on Day 1

Etoposide: 100 mg/m² on Days 1-3

Patients may be treated in up to five NC dosing cohorts (i.e., venetoclax 200 mg Days 1–7 NC, 400 mg Days 1–7 NC, 800 mg Days 1–7 NC, 800 mg Days 1–14 NC, and any of the dose levels integrating primary prophylactic growth factor support). Specifically, at the initiation of the induction phase of dose-escalation Arm B, cohorts will be treated without primary prophylactic growth-colony stimulating factor (G-CSF). If, after review of available data, the MTD is exceeded in a specific cohort due to DLTs associated with a high frequency of febrile neutropenia, severe neutropenia or prolonged neutropenia, then that cohort level will be tested again at the same dose with primary prophylactic growth factor support (see protocol for additional details). Of note, primary G-CSF prophylaxis is only mandated during induction and not during maintenance therapy. Such cohorts will be designated with "-P" to denote the primary G-CSF prophylactic requirement (e.g., Cohort B1-P). Subsequent dose-escalation cohorts will then be required to incorporate primary G-CSF prophylaxis.

Patients will be treated for a total of 4 cycles of study treatment for induction. Each cycle will consist of 21 days. Dose-escalation will continue until DLTs are observed. If there is excessive

Venetoclax—F. Hoffmann-La Roche Ltd Page 19 of 214 Protocol GO41864, Version 2 toxicity and DLTs at the lowest tested venetoclax dose in induction, then venetoclax will be subsequently expanded in the maintenance setting only.

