If 2 or more of the first 6 DLT-evaluable patients in the cohort experience a DLT, an additional 3 patients will be evaluated for DLTs at a lower NC dose level. If none of the first 3 DLT-evaluable patients experiences a DLT, the MTD in maintenance will have been reached.

If 1 of the first 3 DLT-evaluable patients experiences a DLT, the NC dose level cohort will be expanded to 6 patients. If there are no further DLTs in the first 6 DLT-evaluable patients, the MTD in maintenance will have been reached.

If 2 or more of the first 6 DLT-evaluable patients in the NC dose-escalation cohort experience a DLT, the MTD will have been exceeded and dose-escalation in maintenance will stop.

If the MTD is exceeded at any dose level, the highest dose at which fewer than 2 of 6 DLT-evaluable patients (i.e., \geq 33%) experience a DLT will be declared the MTD.

If the MTD is not exceeded at any dose level, the highest dose of venetoclax (800 mg) administered in maintenance will be declared the MTD for the maintenance setting.

Arm B (Refer to protocol):

A minimum of 3 DLT-evaluable patients will initially be enrolled into each cohort.

If none of the first 3 DLT-evaluable patients experiences a DLT, enrollment of the next cohort at the next dose level may proceed.

If 1 of the first 3 DLT-evaluable patients experiences a DLT, the cohort will be expanded to 6 patients. If there are no further DLTs in the first 6 DLT-evaluable patients, enrollment of the next cohort at the next dose level may proceed.

If 2 or more of the first 6 DLT-evaluable patients in the next cohort at the next dose level experience a DLT, the MTD in induction will have been exceeded and dose-escalation will stop.

If the MTD is exceeded at any dose level, the highest dose at which fewer than 2 of 6 DLTevaluable patients (i.e., \geq 33%) experience a DLT will be declared the MTD. If the MTD is not exceeded at any dose level, the highest dose of venetoclax (800 mg NC Day 1–7) administered in induction will be declared the MTD for the induction setting.

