- Induction Cohort B3 (Dose Level 3): Venetoclax: 800 mg/QD NC on Days 1–7 Atezolizumab: 1200 mg Q3W on Day 1 Carboplatin: AUC 5 mg/mL min (Calvert formula) on Day 1 Etoposide: 100 mg/m² on Days 1–3
- Induction Cohort B4 (Dose Level 4): Venetoclax: 800 mg/QD NC on Days 1–14 Atezolizumab: 1200 mg Q3W on Day 1 Carboplatin: AUC 5 mg/mL min (Calvert formula) on Day 1 Etoposide: 100 mg/m² on Days 1–3

Figure 4 Study Schema: Dose-Escalation, Induction (Arm B)

Note: Cohorts may incorporate primary prophylactic growth factor support as described below and in Section 3.1.4.

DLT = dose-limiting toxicity; MTD = maximum tolerated dose; NC = non-continuous; RP2D-I = recommended Phase II dose for induction.

Patients may be treated in up to five NC dosing cohorts (i.e., venetoclax 200 mg Days 1–7 NC, 400 mg Days 1–7 NC, 800 mg Days 1–7 NC, 800 mg Days 1–14 NC, and any of the dose levels integrating primary prophylactic growth factor support). Specifically, at the initiation of the induction phase of dose–escalation Arm B, cohorts will be treated without primary prophylactic growth-colony stimulating factor (G-CSF). If 2 or more patients out of the first 6 DLT-evaluable patients in a particular cohort without primary prophylactic growth factor support experienced neutropenia-related adverse events (Grade 4 neutropenia resulting in treatment delay beyond 14 days or Grade 3–4 febrile neutropenia), then that particular cohort level will be tested again at the same dose *level* with mandatory primary prophylactic growth factor support (see Section 3.1.4 for additional details). Of note, primary G-CSF prophylaxis is only mandated during induction and not during maintenance therapy. Such cohorts will be designated with "-P" to denote the primary G-CSF prophylactic requirement (e.g., Cohort B1-P). Subsequent dose–escalation cohorts will then be required to incorporate primary G-CSF prophylaxis.

Patients will be treated for a total of 4 cycles of study treatment for induction. Each cycle will consist of 21 days. Dose-escalation will continue until DLTs are observed. If there is excessive toxicity and DLTs at the lowest tested venetoclax dose in induction, then venetoclax will be subsequently expanded in the maintenance setting only.

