Arm B (Refer to Figure 4):

- A minimum of 3 DLT-evaluable patients will initially be enrolled into each cohort.
- If none of the first 3 DLT-evaluable patients experiences a DLT, enrollment of the next cohort at the next dose level may proceed.

Venetoclax—F. Hoffmann-La Roche Ltd Page 58 of 214 Protocol GO41864, Version 1

- If 1 of the first 3 DLT-evaluable patients experiences a DLT, the cohort will be expanded to 6 patients. If there are no further DLTs in the first 6 DLT-evaluable patients, enrollment of the next cohort at the next dose level may proceed.
- If 2 or more of the first 6 DLT-evaluable patients in the next cohort at the next dose level experience a DLT, the MTD in induction will have been exceeded and doseescalation will stop.
- If the MTD is exceeded at any dose level, the highest dose at which fewer than 2 of 6 DLT-evaluable patients (i.e., ≥ 33%) experience a DLT will be declared the MTD.

If the MTD is not exceeded at any dose level, the highest dose of venetoclax (800 mg NC Day 1-14) administered in induction will be declared the MTD for the induction setting.

If a particular cohort in induction dose-escalation (Arm B) exceeds MTD due to DLTs associated with neutropenia or febrile neutropenia without primary prophylactic growth factor support, then that cohort level will be tested again with primary prophylactic growth factor support. For example, if venetoclax 400 mg Day 1–7 exceeds the MTD due to DLTs associated with neutropenia or febrile neutropenia without primary prophylactic growth factor support, then primary prophylactic growth factor support will be implemented in the study and that dose level cohort will be tested again with another 3+3 cohort. Of note, primary G-CSF prophylaxis is only mandated during induction and not during maintenance therapy. Once prophylactic growth factor support is instituted, then this will be required for further escalation cohorts during all induction cycles. For guidance on use of prophylactic growth factor support, please see Appendix 10.

Patients exhibiting acceptable safety and evidence of clinical benefit (as determined by the investigator) may continue to receive study treatment until confirmed objective disease progression or unacceptable toxicity, whichever occurs first.

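### The MTD rule contradicts itself: its bracketed percentage reverses the stated threshold in four places, and the synopsis names the wrong top induction regimen

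*Combined protocol and SAP*

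**What the plan says.** Section 3.1.4 lists the dose-escalation rules for Arm A (maintenance) and Arm B (induction). For each arm it says that, once some level has exceeded the MTD, "the highest dose at which fewer than 2 of 6 DLT-evaluable patients (i.e., ≥ 33%) experience a DLT will be declared the MTD". The synopsis repeats the sentence, with the same bracket, for Arm A and for Arm B. That makes four places.

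The bullets around this sentence set the direction. In Arm B the condition for the MTD being exceeded begins: "If 2 or more of the first 6 DLT-evaluable patients in the next cohort at the next dose level experience a DLT". In Arm A the same count, 2 or more of 6, sends the study to a lower dose level.

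Both places also say what happens if no induction level exceeds the MTD. The synopsis says "the highest dose of venetoclax (800 mg NC Day 1–7) administered in induction will be declared the MTD". Section 3.1.4 says "the highest dose of venetoclax (800 mg NC Day 1-14) administered in induction will be declared the MTD".

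The planned induction levels are not in doubt. Section 3.1.2.2 gives the last one as "Induction Cohort B4 (Dose Level 4): Venetoclax: 800 mg/QD NC on Days 1–14". The synopsis cohort list ends the same way: "800 mg Days 1–7 NC, 800 mg Days 1–14 NC, and any of the dose levels integrating primary prophylactic growth factor support".

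**The concern.** An i.e. bracket should restate the condition it follows. Here it gives a percentage range that the condition excludes, in the sentence that defines the MTD. Separately, the synopsis and the body name two different planned cohorts as the MTD when every induction level clears.

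MTD estimation is part of the primary dose-escalation objective (Section 2.1.1), and Section 3.1.4 bases the induction RP2D on the induction MTD. An investigator, ethics committee or regulator should not have to work out which half of a sentence, or which of two sections, is the rule. Followed literally, the synopsis would set aside a top level that had cleared and declare the level below it.

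**Working it through.** **1. The bracket.** Inputs: the threshold of fewer than 2 of 6 and the bracket of ≥ 33%, both from the rule sentence in Section 3.1.4 and the synopsis. Each possible count k out of six is converted to a percentage, 100 × k/6:

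| DLTs out of 6 | Percentage | Fewer than 2 of 6? | ≥ 33%? |
|---|---|---|---|
| 0 | 0% | yes | no |
| 1 | 16.7% | yes | no |
| 2 | 33.3% | no | yes |
| 3 | 50.0% | no | yes |
| 4 | 66.7% | no | yes |
| 5 | 83.3% | no | yes |
| 6 | 100% | no | yes |

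No row has yes in both columns, so the two conditions are exact complements. The figure 33% does correspond to 2/6, the count at which a level fails, so the number is right and the direction is wrong.

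**2. The top induction regimen.** The relevant places, side by side:

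| Place | What it gives |
|---|---|
| Synopsis, Arm B rules | default MTD is 800 mg, Day 1–7 |
| Section 3.1.4, Arm B rules | default MTD is 800 mg, Day 1–14 |
| Synopsis, cohort list | B3 is Days 1–7; B4, Dose Level 4, is Days 1–14 |
| Section 3.1.2.2, cohort list | the same: B4 is Days 1–14 |
| Section 3.3.2.2, dose rationale | escalation ends at 800 mg, Day 1–14 |
| Appendix 2, footnote cc | induction venetoclax for 7 or 14 days |

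The synopsis rule is the outlier. It contradicts the cohort list in the same synopsis. The difference is 7 against 14 venetoclax days per 21-day cycle at the same daily dose.

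**3. How often the disputed sentence would apply.** It applies only if all four induction levels clear. Under the stated rules a level clears with 0 of 3 DLTs, or with 1 of 3 followed by 0 of the next 3. For a true DLT rate p:

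P(clear) = (1−p)³ + 3p(1−p)² × (1−p)³

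The documents give no DLT rate. Assuming one constant rate across B1 to B4, and ignoring the G-CSF retest cohorts, the chance that all four clear is P(clear)⁴:

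| Assumed p | One level clears | All four clear |
|---|---|---|
| 5% | 0.973 | 0.898 |
| 10% | 0.906 | 0.674 |
| 20% | 0.709 | 0.252 |
| 30% | 0.494 | 0.060 |

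Worked for p = 0.20: 0.8³ = 0.512; 3 × 0.2 × 0.64 = 0.384; 0.512 + 0.384 × 0.512 = 0.709; 0.709⁴ ≈ 0.25.

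These figures are the probability that the sentence comes into play. They are not the probability of a wrong dose.

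**The case against.** The strongest reply is that these are copy-edits. The operative words are the patient counts. The bracket sits directly after 2 of 6 and can be read as a misplaced note that 2 of 6 is 33%. Nobody could apply it literally, because it would declare as MTD a level that the adjacent bullets have just failed. On the second point, the synopsis Arm B rules refer the reader to the protocol, Section 3.1.4 is correct, and the sentence itself speaks of the highest dose administered. The RP2D decision is led by the Medical Monitor with the Principal Investigators and a committee that includes a statistician, and it integrates aggregate safety data.

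Most of this stands, and it is why the practical weight is minor. It does not make the text right: an i.e. that states the complement of its own rule is an error however it arose, and the two default regimens cannot both hold.

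Three narrower criticisms are also fair.

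- A constant DLT rate from 200 mg for 7 days to 800 mg for 14 days is implausible, so the probabilities are illustrative only.
- On the Arm B path a cohort expands to six only after exactly 1 of 3, so only 1/6 to 4/6 can occur there. The two conditions still share no result in that range.
- The synopsis Arm A rules keep other stale wording: they still call the lower dose level NC, although Arm A dosing is continuous and Section 3.1.4 no longer uses the term. That belongs in the same clean-up and does not weaken either point.

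**Conclusion.** Both points hold, and both are in current protocol text. The bracket reverses the MTD threshold in four places: the counts allow 0% or 16.7%, the bracket allows 33.3% to 100%, and they share no outcome. The synopsis names Cohort B3 as the default induction MTD where Section 3.1.4 and every listing of the planned cohorts point to Cohort B4.

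The consequence is limited. The bracket alone should not change a dose decision. The synopsis error could lead a reader to declare the MTD one level too low, but only if all four levels clear, and it points to less exposure, so it is not an overdosing hazard. No sample size, cohort dose, DLT definition or analysis is affected. The comparison of the texts needs no assumptions; only the probabilities in the third step do. Because the errors sit in a decision rule for the primary dose-escalation objective, they should be corrected.

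**What to change.** Replace the bracket with (i.e., < 33%, at most 1 of 6) in all four places: synopsis Arm A, synopsis Arm B, Section 3.1.4 Arm A and Section 3.1.4 Arm B. In the synopsis Arm B rule, replace 800 mg NC Day 1–7 with 800 mg NC Day 1–14, to match Section 3.1.4 and Cohort B4. While the synopsis is open, its Arm A rules can drop the leftover NC wording to match Section 3.1.4.

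The cost is five wording edits, plus the optional tidying. No patients, visits or DLT windows are added, and no cohort dose or 3+3 rule changes.
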